8.6.1. Extent of Exposure

Descriptive information will be provided by treatment arm regarding the duration of exposure to study drug, and the number and timing of dose interruptions and reductions.

8.6.2. Adverse Events

All AEs will be listed. The focus of AE summarization will be on treatment-emergent AEs. A treatment-emergent AE is defined as any AE with onset date on or after the date of first dose of study drug up to 30 days after permanent study drug discontinuation or any AEs leading to premature study drug discontinuation.

AEs will be classified using Medical Dictionary for Regulatory Activities with descriptions by system organ class (SOC), high-level group term, high-level term, preferred term (PT), and lower-level term. The severity of AEs will be graded by the investigator according to the CTCAE, Version 5.0, whenever possible. If a CTCAE criterion does not exist for a specific type of AE, the grade corresponding to the appropriate adjective will be used by the investigator to describe the intensity of the AE: Grade 1 (mild), Grade 2 (moderate), Grade 3 (severe), Grade 4 (life threatening), or Grade 5 (fatal). The relationship of the AE to the study drug will be categorized as related or unrelated.

For the primary safety endpoint, the number and percentage of subjects who experienced at least one Grade ≥ 4 TEAE will be listed and summarized by SOC and PT, and by treatment arm in the Safety Analysis Set. The severity, timing, relationship to study drug, drug interruptions, reductions, and discontinuations for Grade ≥ 4 TEAEs will be summarized.

Summaries (number and percentage of subjects) of TEAEs by SOC and PT will be provided. A subject who reports multiple TEAEs within the same PT (or SOC) is counted only once for that PT (or SOC) using the worst severity grade. AE descriptions will be presented by decreasing frequency for a given SOC and PT.

Separate summaries will be prepared for the following types of TEAEs:

- Idelalisib-related AEs
- AEs that are Grade ≥ 4 in severity

- AEs that are Grade ≥ 3 in severity
- AEs leading to study drug interruption, reduction, or discontinuation
- SAEs

Additional analysis on AEs will be performed. The AEs include: Grade ≥ 3 diarrhea/colitis, rash, febrile neutropenia, infection, and any grade of the following: pneumonitis, bowel perforation, progressive multifocal leukoencephalopathy (PML), PJP, CMV infection, and organizing pneumonia. The frequency, severity, timing, and drug interruptions for AEs will be summarized by treatment arm using descriptive statistics. Time to first onset of AEs and time to resolution will be summarized using the Kaplan-Meier method.

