
Duration of Treatment:
	
Idelalisib will be administered continuously until the earliest of: disease progression, unacceptable toxicity, substantial noncompliance with study procedures or study drug, initiation of another systemic anti-cancer or experimental therapy, or withdrawal from the study.

Duration of Study:
	
The overall duration of the study is expected to be approximately 10 years.

Eligibility Criteria:
	
Inclusion Criteria
 
Subjects must meet all of the following inclusion criteria to be eligible for participation in this study:
 
 1) Male or female ≥ 18 years of age 2) Histologically confirmed diagnosis of B-cell FL, and grade limited to 1, 2, or 3a based on criteria established by the World Health Organization (WHO) 2008 classification of tumors of hematopoietic and lymphoid tissues 3) Relapsed or refractory FL and have received at least 2 lines of prior therapy for FL and have no other available therapeutic options. Note: Rituximab maintenance is not routinely considered a separate line of therapy when it is given as part of the prior rituximab-containing regimen given over a number of cycles followed by maintenance. Rituximab monotherapy may be considered a separate line of therapy when disease relapse occurs between the initiation of rituximab monotherapy and the preceding line of therapy. If there are any ambiguities about eligibility, the site should consult with the medical monitor. 4) Ann Arbor Stage 2 (noncontiguous), 3, or 4 disease per Lugano Classification 5) Radiographically measurable lymphadenopathy or extranodal lymphoid malignancy as determined by IRC, defined as the presence of at least 1 lesion that measures ≥ 1.5 cm in the longest dimension [LD] and ≥ 1.0 cm in the longest perpendicular dimension as assessed by positron emission tomography-computed tomography [PET-CT], computed tomography [CT], or magnetic resonance imaging [MRI]) 6) Have adequate performance status (such as Eastern Cooperative Oncology Group Performance Status of ≤ 2 or Karnofsky Performance Status of ≥ 60) 7) Required baseline laboratory data (within 4 weeks prior to start of study therapy) as shown in the table. Note: Confirmation should be considered for out-of-range values to determine if the abnormality is real or artifactual. Values should be obtained within the screening period and should generally be the most recent measurement obtained. 												

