1.4. Risk/Benefit Assessment for the Study

Anticipated Benefits

This study randomizes patients with FL to one of 2 idelalisib regimens, the approved regimen or the alternative regimen. The alternative regimen with an intermittent dosing schedule (Arm C), results in lower idelalisib exposure, and thus has the potential for decreased frequency and severity of TEAEs. Subjects on the alternate regimen may thus benefit from reduced toxicity and fewer dose interruptions. Since the study requires response assessments on a 12-week schedule during the first 15 months of study treatment, a lack of response or progression of disease will be identified in a subject's treatment course. Consequently, while there is the possibility of decreased efficacy in Arm C, the risk to the individual subject is minimized by the response assessment schedule, with the option for subjects on Arm C to discontinue treatment.

Anticipated Risks

In 2016, an increased risk of death and a higher incidence of serious adverse events (SAEs), predominantly infectious events, were observed among subjects receiving idelalisib in combination with standard therapies compared to the control groups in a pooled analysis conducted by the independent data monitoring committee (DMC) of 3 Phase 3 clinical studies in patients with first-line CLL and early-line iNHL. Global regulatory agencies were notified of these findings and independently reviewed the data. These reviews confirmed a positive benefit-risk profile of Zydelig[®] (idelalisib) in the approved indications. Zydelig[®] country product labels were subsequently updated to include measures to minimize the risk of serious infections, including *Pneumocystis jirovecii* pneumonia (PJP) prophylaxis and cytomegalovirus (CMV) monitoring, in line with the risk minimization measures employed in clinical studies.

While CMV and PJP are important risks, these pathogens accounted for a relatively small proportion of the serious infections observed; therefore, more general measures are also used to minimize the risk of serious infections. In particular, treatment should not be initiated in subjects with evidence of ongoing systemic infection and subjects should be monitored for respiratory signs and symptoms throughout treatment and advised to report new respiratory symptoms promptly. Subjects should be administered PJP prophylaxis as described in Section 7.5.6.

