8.2. Analysis Conventions

The primary study analysis will be conducted when all enrolled subjects have discontinued the study or been on treatment for at least 48 weeks and completed response assessment of Week 48.

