1. INTRODUCTION

This statistical analysis plan (SAP) describes the statistical analysis methods and defines key elements including variable definitions for analysis of data of Study *GS-US-313-1580* in support of the clinical study report (CSR). This SAP is based on the study protocol *amendment 6* dated *18 March 2021*. Any changes made after the finalization of the SAP will be documented in the CSR.

This study was designed to evaluate a safe and effective dosing regimen of idelalisib in subjects with relapsed or refractory Follicular Lymphoma (FL) who have no other therapeutic options. It is a randomized, open-label, multi-center global study with three treatment arms in total of 266 subjects planned. The study was terminated early due to slow enrollment, with rapidly evolving treatment options for FL as the primary reasons.

Analysis methods specified in this document take precedence over those described in protocol should there be any difference.

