7.1.5. Treatment-Emergent Adverse Events

7.1.5.1. Definition of Treatment-Emergent Adverse Events

Treatment-emergent adverse events (TEAEs) are defined as 1 or both of the following:

- Any AEs with an onset date on or after the study drug start date and no later than 30 days after permanent discontinuation of study drug
- Any AEs leading to permanent discontinuation of study drug.

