7.1.6.1. Summaries of Adverse Events Incidence by Severity

The number and percentage of subjects who experienced at least 1 TEAE will be provided and summarized by SOC and PT.

The number and percentage of subjects who experienced at least 1 TEAE will be provided and summarized by PT and severity in descending order of total frequency:

- Treatment-Emergent Adverse Events by PT and Severity

For the AE categories described below, summaries will be provided by PT in descending order of total frequency:

- All Treatment-Emergent Adverse Events
- Grade 4 or Higher Treatment-Emergent Adverse Events
- Grade 3 or Higher Treatment-Emergent Adverse Events
- Treatment-Emergent Idelalisib related Adverse Events
- Treatment-Emergent Serious Adverse Events
- Treatment-Emergent Idelalisib related Serious Adverse Events
- Treatment-Emergent Adverse Events leading to discontinuation of Idelalisib
- Treatment-Emergent Adverse Events leading to temporary interruption of Idelalisib
- Treatment-Emergent Adverse Events leading to study discontinuation
- Treatment-Emergent Adverse Events leading to Death

A brief, high-level summary of AEs described above will be provided by treatment arms and by the number and percentage of subjects who experienced the above AEs.

For summaries of TEAEs by PT, multiple events will be counted only once per subject in each summary. Adverse events will be summarized and listed by PT in descending order of total frequency. For summaries by severity, the most severe severity will be used for those AEs that occurred more than once in a given subject during the study.

In addition, by-subject data listings will be provided by treatment arms and subject ID number in ascending order for the following:

- All AEs, indicating whether the event is treatment emergent
- All SAEs
- All Deaths
- All Adverse Events leading to Death
- All Adverse Events with Grade 3 or Higher
- All Adverse Events with Grade 4 or Higher

- All Adverse Events leading to discontinuation of Idelalisib
- All Adverse Events leading to temporary interruption of Idelalisib
- All Adverse Events leading to study discontinuation

A flag will be included in the listings to indicate whether the event is treatment emergent.

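### The primary safety endpoint is a crude percentage over subject-specific treatment time, and the SAP adds no time-based estimate that would let the arms be compared as toxicity rates if time on treatment differs

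*Protocol*

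**What the plan says.** - **Endpoint.** Protocol 8.6.2 gives the analysis as "For the primary safety endpoint, the number and percentage of subjects who experienced at least one Grade" 4 or higher TEAE, by SOC, PT and arm, in the Safety Analysis Set. Its next sentence adds that severity, timing, relationship, interruptions, reductions and discontinuations of these events will be summarised.
- **SAP delivery.** In SAP 7.1.6.1, Grade 4 or higher TEAEs are one item in a list introduced by "For the AE categories described below, summaries will be provided by PT in descending order of total frequency". A high-level table of subject counts and percentages by arm and a by-subject listing accompany it. There is no timing table.
- **Window.** SAP 7.1.5.1 counts events with onset "no later than 30 days after permanent discontinuation of study drug" (or leading to permanent discontinuation).
- **Treatment length.** The protocol synopsis says: "Idelalisib will be administered continuously until the earliest of: disease progression, unacceptable toxicity, substantial noncompliance with study procedures or study drug", start of another systemic therapy, or withdrawal.
- **Exposure.** Protocol 8.6.1 and SAP 4.2 summarise duration by arm descriptively. Neither uses it as a denominator.
- **Time to onset.** SAP 7.6 states that the protocol's time-to-onset analysis for adverse events of interest was not performed. SAP 1 gives the SAP precedence where the two documents differ.
- **Purpose.** Protocol 1.3 sets the goal of learning whether the alternative regimen can match the efficacy of the approved one with less toxicity.

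**The concern.** A proportion of subjects who ever had an event on treatment rises with time at risk. Two arms with the same event rate per month show different percentages if subjects leave one of them sooner for reasons other than a Grade ≥ 4 event, such as progression or lower-grade toxicity.

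Protocol 1.4 gives grounds to expect that this could happen, in either direction. It says "while there is the possibility of decreased efficacy in Arm C", which would shorten treatment through earlier progression. It also expects that Arm C may be less toxic, which could lengthen treatment. Arm B had a further asymmetry. Its subjects with SD or PD could escalate and stay on drug, while 150 mg subjects enrolled before Amendment 5 stopped at PD (Protocol 3.2.2).

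At stake is the reading of a primary endpoint in a regimen-selection trial. A schedule that subjects leave early could look safer than it is, and one that they tolerate for longer could have a real benefit hidden.

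**Working it through.** **The plan's own figure.** Protocol 8.8 states a 95% CI half-width of at most 10% for a Grade ≥ 4 TEAE rate of 20%-40% with 120 subjects. Clopper-Pearson gives 7.5% at 24/120, 8.5% at 36/120 and 9.1% at 48/120, so the statement holds. The issue is not arithmetic.

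**Inputs.** The reference incidence is 23/72 = 32% (Protocol 1.3, FL subjects in Study 101-09), and n is 120 per arm (Protocol 8.8). The 30-day tail is taken as 1 month. Mean time on treatment T is *assumed* to be 6, 9 or 12 months in the longer-treated arm, because the documents give none. Both arms have the same hazard λ, set so that the longer-treated arm shows 32%.

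**Formulas, constant hazard.**
- Fixed duration: p = 1 − exp(−λ(T + 1)), with λ = −ln(0.68)/(T + 1) in the longer arm.
- Exponential stopping with mean T: p = 1 − exp(−λ) × (1/T)/((1/T) + λ).

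**Worked case, T = 9, fixed duration.** λ = 0.3857/10 = 0.0386 per month. At 6.75 months, p = 1 − exp(−0.0386 × 7.75) = 25.8%. At 4.5 months, p = 1 − exp(−0.0386 × 5.5) = 19.1%.

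**Front-loaded variant.** The hazard after month 4 is 25% of the early hazard. In the fixed-duration formula, T + 1 is replaced by min(T + 1, 4) + 0.25 × max(0, T + 1 − 4). For exponential stopping the same cumulative hazard is integrated over the stopping time.

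| Spurious difference from 32%, T = 6 to 12 | 25% shorter | 50% shorter |
|---|---|---|
| Constant hazard, exponential stopping | 5.0-5.4 points | 10.9-11.8 points |
| Constant hazard, fixed duration | 5.9-6.3 | 12.2-13.3 |
| Front-loaded, exponential stopping | 3.0-3.4 | 6.8-7.4 |
| Front-loaded, fixed duration | 2.1-3.2 | 4.3-6.6 |

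If every event fell within the first 4 months and all subjects stayed that long, the difference would be zero.

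**Opposite direction.** Take T = 9, exponential stopping, a true rate 25% lower and treatment 1.33 times as long. The crude result is 31.2% against 32.0%. At equal duration it would be 25.9%.

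**Precision of a comparison.** 1.96 × √(2 × 0.32 × 0.68/120) = 11.8 points.

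**Do the candidate remedies remove the artefact?** Identical regimens, mean 9 against 4.5 months, exponential stopping:
- *Kaplan-Meier censored at end of window* (constant hazard): 22.0% at Week 24 and 39.2% at Week 48, the same in both arms. With 120 per arm about 24 and 8 subjects remain at risk at Week 48, so the late estimate is imprecise.
- *Exposure-adjusted rate*: 4.5 against 4.5 per 100 subject-months under a constant hazard, but 4.5 against 5.7 under the front-loaded one. Split at Week 24, the front-loaded case gives 6.7 against 7.0 before and 2.0 against 2.0 after, so the split removes most of the distortion.
- *Cumulative incidence with end of window as a competing event* (constant hazard): about 26% against 19% at Week 48. The artefact remains.

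**The case against.** Several points on the other side stand.

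- **Unequal time is not documented.** A reader might infer that the arms did differ in exposure, or that the endpoint will favour Arm C. The documents support neither. They give no duration by arm, Protocol 1.4 calls reduced efficacy hypothetical, and the two plausible mechanisms push in opposite directions.
- **The protocol is not silent on time.** It would be too strong to say that only percentages were ever planned, since Protocol 8.6.2 promises a timing summary. SAP 7.6 names only the time-to-onset analysis for adverse events of interest as dropped. The fair criticism is that timing was promised and not put into operation.
- **Many events may be early.** Transaminase elevations are minimal beyond 4 months (Protocol 1.3) and opportunistic infections occur mostly within 6 months (Protocol 7.5.6). The most frequent Grade ≥ 4 events listed in Protocol 1.3 do not include colitis or pneumonitis. This reduces the artefact. It probably does not remove it: Protocol 1.3 describes Grade ≥ 3 diarrhea/colitis as continuing through treatment and pneumonitis up to 14.1 months, although neither figure is specific to Grade ≥ 4.
- **The plan is descriptive.** No formal test is planned (SAP 3.5), and lost efficacy would show in ORR and PFS. Readers will still set the two percentages side by side, because that is the trial's stated purpose.
- **The crude proportion is legitimate.** It describes the chance of an event while on treatment, and an exit caused by a Grade ≥ 4 event is counted. It is just not a rate.

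**Conclusion.** The concern holds as a conditional statement about the estimator. If time on treatment differs between arms, the crude Grade ≥ 4 percentages are not comparable as toxicity rates, and the SAP contains nothing that would show this. Under the stated assumptions the distortion is 5 to 6 points for 25% shorter treatment and 11 to 13 for 50% shorter. With a front-loaded hazard it is about 2 to 3 and 4 to 7.

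A reader might conclude that such an artefact would dominate the comparison. At 25% shorter treatment it is well below the 11.8-point half-width for a between-arm difference. It is, however, a systematic shift, and that interval does not account for it. Precision may also be lower than at 120 per arm: "The study was terminated early due to slow enrollment" (SAP 1). The actual direction and size cannot be established from the documents.

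**What to change.** Keep the crude proportion as the primary summary. Add to SAP 7.1.6.1, by arm and labelled supportive:

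1. **Time to first Grade ≥ 4 TEAE by Kaplan-Meier**, censored at the end of the treatment-emergent window (or at data cut-off if still on treatment), with estimates, 95% CIs and numbers at risk at Weeks 24 and 48. State that it assumes non-informative stopping.
2. **Exposure-adjusted rate of first Grade ≥ 4 TEAE with 95% CI**, counting time to first event or end of window. State that it assumes a roughly constant hazard, and show it by period (for example before and after Week 24) because early events are expected.

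Do not use cumulative incidence with end of window as a competing event for this purpose, because it keeps the artefact. The first analysis would also go some way to meeting the timing summary promised in Protocol 8.6.2.

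The cost is two tables and a few SAP sentences. The dosing and onset dates are already derived (SAP 4.2 and 7.1.5.2). The SAP has been signed, so the additions would be documented in the CSR, as SAP 1 provides. The downside is that each added estimate rests on its stated assumption, and late Kaplan-Meier estimates may rest on few subjects.

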8.6.3. Laboratory Evaluations

All laboratory data will be listed. Summaries of laboratory data will be based on observed data. The focus of laboratory data summarization will be on treatment-emergent laboratory abnormalities. A treatment-emergent laboratory abnormality is defined as an abnormality that, compared to baseline, worsens by ≥ 1 grade in the period from the first dose of study treatment (idelalisib) to 30 days after the last dose of study treatment. If baseline data are missing, then any graded abnormality (ie, an abnormality that is Grade ≥ 1 in severity) will be considered treatment emergent.

Hematological and serum biochemistry data will be programmatically graded according to CTCAE severity grade, when applicable. Hematological and serum biochemistry and their changes from baseline will be summarized by treatment and by visit. Summary tables will be presented for each relevant assay to show the number of subjects by CTCAE severity grade with corresponding percentages. For parameters for which a CTCAE scale does not exist, the frequency of subjects with values below, within, and above the normal ranges will be summarized. Subjects will be characterized only once for a given assay, based on their worst severity grade observed during a period of interest (eg, during the study or from baseline to a particular visit). Shift tables for hematology and serum biochemistry will also be presented by showing change in CTCAE severity grade from baseline to the worst grade post baseline. Separate listings and summaries will be prepared for laboratory abnormalities that are Grade ≥ 3 in severity.

8.7. Pharmacokinetic Analysis

Plasma concentrations of idelalisib/metabolite will be listed and summarized by treatment arm and visit using descriptive statistics (eg, sample size, arithmetic mean, geometric mean, % coefficient of variation, StD, median, minimum, and maximum).

Additionally, a population PK model using a nonlinear mixed-effect modeling technique may be used to characterize the PK of idelalisib and GS-563117. Idelalisib exposure-response relationship between efficacy, safety, and idelalisib and/or GS-563117 exposure may be explored.

A logistic regression model may be used to explore the correlation between drug exposure and efficacy or safety.

8.8. Sample Size

The planned sample size is approximately 266 subjects: approximately 120 subjects in Arm A, approximately 26 subjects in Arm B, and approximately 120 subjects in Arm C. As of Protocol Amendment 5, Arm B enrollment was closed after enrollment of approximately 26 subjects into Arm B and approximately 26 subjects into Arm A.

As of Protocol Amendment 5, subjects will be randomized to 2 arms (Arm A and C) with a 1:1 ratio until the enrollment target of 120 subjects in each arm is met. The ORR was approximately 56% for subjects with FL in Study 101-09. If the underlying true ORR is 56% for subjects in this study, the chance to observe 60 or more responders out of 120 subjects (observed $ORR \geq 50\%$) is 92%. With 120 subjects in each arm, the half-width of a two-sided 95% CI of ORR is $\leq 10\%$ for an observed ORR in the range of 40%-60%, and the half-width of a two-sided 95% CI of \geq Grade 4 TEAEs incidence rate is $\leq 10\%$ for an observed AE rate in the range of 20%-40%.

The sample size was originally planned to include 240 subjects randomized to Arm A and Arm B with a 1:1 ratio. The previous sample size calculation is based on the rate of Grade ≥ 3 diarrhea/colitis approximately 15% in the prior idelalisib studies. A sample size of 120 subjects per arm would provide 73% chance to detect a reduction of 10% (ie, 15% incidence in the 150 mg twice daily arm versus 5% incidence in the 100 mg twice daily arm) using a 2-sided Chi-square test with alpha level of 0.05.

